1.2 Protocol Synopsis

Title	Long-term Outcomes of Children with Hypoplastic Left Heart Syndrome and the Impact of Norwood Shunt Type (SVR III)
Study Objectives	
 1. To determine if shunt type at the time of Norwood operation is associated with long-term differences in cardiac function, survival or contributors to quality of life. 2. To characterize long-term outcomes and determine risk factors other than shunt type for adverse long term outcomes in children with hypoplastic left heart syndrome (HLHS) and other related single ventricle anomalies.
Significance	The proposed long-term follow-up of the Single Ventricle Reconstruction (SVR) trial cohort is required to determine the optimal shunt approach for children with HLHS.
Study Design	Prospective follow-up study of the SVR cohort
Primary Aim	To compare direct and indirect measures of right ventricular (RV) systolic and diastolic function between 11 year old subjects who had been randomly assigned to receive a right ventricle to pulmonary artery shunt (RVPAS) vs. a modified Blalock-Taussig shunt (MBTS) at the time of the Norwood operation.
Secondary Aim(s)	
 1. To compare the incidence of death or cardiac transplantation between those randomized to receive a RVPAS vs. a MBTS at the time of the Norwood operation. 2. To compare exercise tolerance between those randomized to a RVPAS vs. a MBTS. 3. To compare the incidence of arrhythmias between those randomized to a RVPAS vs. a MBTS. 4. To compare neurodevelopmental outcomes at 11 years of age in those randomized to a RVPAS vs. a MBTS 5. To develop risk stratification models for 1) cardiac outcomes, 2) transplant-free survival, and 3) neurodevelopmental outcomes. 6. To collect specimens from subjects and their parents to further develop the biologic specimen repository.
Accrual Objective	Fixed cohort, ideally with a 2 year window for participation (11 \pm 1 year of age), but subjects can be enrolled at any time there is interest in participation up until September 30, 2020.
Study Duration	10.5 years (June 2015 - November 2025)
Inclusion Criteria	Transplant-free survivors of the SVR cohort (All SVR survivors are eligible to be followed for vital status.)
Exclusion Criteria	Participants who received cardiac transplantation or biventricular conversion will be excluded from all outcomes other than vital status.

1.4 List of Abbreviations

ABAS	Adaptive Behavior Assessment System
AE	Adverse Event
AUC	Area under the Curve
BRIEF	Behavior Rating Inventory of Executive Function
CEC	Clinical Events Committee
CI	Confidence Interval
CMR	Cardiac Magnetic Resonance Imaging
Connors 3 AI	Connors 3 rd Edition Attention Deficit and Hyperactivity Index
CRF	Case Report Form
CTCAE	Common Terminology Criteria for Adverse Events
DCC	Data Coordinating Center
DMP	Data Management Plan
DMS	Data Management System
DSMB	Data and Safety Monitoring Board
DTI	Doppler Tissue Imaging
EC	Executive Committee
Echo	Echocardiogram
eCRF	Electronic Case Report Form
EDC	Electronic Data Capture
FDA	Food and Drug Administration
GCP	Good Clinical Practice
GLP	Good Laboratory Practice
HRQOL	Health-Related Quality of Life
HLHS	Hypoplastic Left Heart Syndrome
IART	Intra-Atrial Reentrant Tachycardia
IB	Investigator's Brochure
ICF	Informed Consent Form
ICH	International Conference of Harmonization
IDE	Investigational Device Exemption
IEC	Independent Ethics Committee
IND	Investigational New Drug
IRB	Institutional Review Board
IV	Intravenous
IVC	Inferior Vena Cava
IVRS	Interactive Voice Response System
IWRS	Interactive Web-based Response System
LPA	Left Pulmonary Artery
MBTS	Modified Blalock-Taussig Shunt
MedDRA	Medical Dictionary for Drug Regulatory Activities
MM	Medical Monitor
MOO	Manual of Operations
MRI	Magnetic Resonance Imaging
ND	Neurodevelopmental
NEPSY-II	A Developmental NEuroPSYchological Assessment – Second Edition
NCBI	National Center for Biotechnology Information
NIH	National Institute of Health
NHLBI	National Heart, Lung and Blood Institute

OHRP	Office for Human Research Protection
Peds-QL	Pediatric Quality of Life Inventory
PC	Phase Contrast
PHN	Pediatric Heart Network
PI	Principal Investigator
QA	Quality Assurance
QC	Quality Control
QOL	Quality of Life
RPA	Right Pulmonary Artery
RV	Right Ventricle
RVED	Right Ventricular End Diastolic
RVEDV	Right Ventricular End Diastolic Volume
RVEF	Right Ventricular Ejection Fraction
RVES	Right Ventricular End Systolic
RVESV	Right Ventricular End Systolic Volume
RVPAS	Right Ventricular to Pulmonary Artery Shunt
SAE	Serious Adverse Event
SC	Steering Committee
SMF	Site Master File
SMP	Site Monitoring Plan
SSFP	Steady State Free Precession
SSL	Secure Socket Layer
SVR	Single Ventricle Reconstruction
SVR II	Single Ventricle Reconstruction Extension Study
SVT	Supraventricular Tachycardia
SVC	Superior Vena Cava
TR	Tricuspid Regurgitation
TV	Tricuspid Valve
VO ₂	Oxygen Consumption
VO ₂ max	Maximum Oxygen Consumption
WIAT	Wechsler Individual Achievement Tests
WISC	Wechsler Intelligence Scale for Children

2. STUDY AIMS AND HYPOTHESES

2.1 Primary Aim:

To compare direct and indirect measures of right ventricular (RV) systolic and diastolic function between 11 year old subjects who had been randomly assigned to receive a right ventricular-to-pulmonary artery shunt (RVPAS) vs. a modified Blalock-Taussig shunt (MBTS) at the time of the Norwood operation.

Hypothesis: Assignment to the RVPAS compared to the MBTS will be associated with worse RV performance in subjects at age 11 years.

Primary Outcome: RV ejection fraction (RVEF) at 11 years, as measured by cardiac magnetic resonance (CMR).

Secondary Outcomes: Secondary outcomes will include additional measures of ventricular systolic, diastolic, and global function by CMR and echocardiogram (echo); anatomic measures related to RV function; and physiologic measures affecting RV function. Secondary outcomes of the greatest importance include:

- RVEF (measured by echo)
- RV fractional area change (measured by echo and CMR)
- Cardiac output (measured by CMR)

2.2 Secondary Aims

Secondary Aim 1: To compare the long-term effect of the RVPAS to that of the MBTS on the incidence of death or cardiac transplantation in children with hypoplastic left heart syndrome (HLHS) and other single RV anomalies undergoing the Norwood procedure.

Hypothesis: The incidence of death or cardiac transplant will be higher in the RVPAS group compared to the MBTS group.

Outcomes:

- The composite of the earliest occurrence of mortality and cardiac transplantation using all available follow-up (ranging from 10 to 15 years).
- Conditional freedom from death or cardiac transplantation by 11 years among subjects who survived >1 year post-randomization.
- Survival at 11 years post-randomization and when the last enrolled subject is 11 years old.
- Transplant at 11 years post-randomization and when the last enrolled subject is 11 years old.
- The composite of the earliest occurrence of mortality, cardiac transplantation and pacemaker placement, using all available follow-up (ranging from 10 to 15 years).

Secondary Aim 2: To compare exercise tolerance between those randomized to receive a RVPAS vs. a MBTS at the time of the Norwood operation.

Hypothesis: Subjects assigned to the RVPAS group will have lower exercise performance at age 11 years compared to those assigned to the MBTS group.

Outcomes:

- Exercise capacity: Maximal Oxygen Consumption (VO₂max), maximal work rate, and anaerobic threshold

Secondary Aim 3: To compare the incidence of arrhythmias between those randomized to receive a RVPAS vs. a MBTS at the time of the Norwood operation.

Hypothesis: The RVPAS will be associated with a greater prevalence of ventricular arrhythmias, but will not differ from the MBTS in the prevalence of atrial arrhythmias.

Outcomes:

- History of ventricular arrhythmias by age 11 years by parent report and with medical record confirmation.
- History of atrial arrhythmia by age 11 years, including intra-atrial reentrant tachycardia (IART) or supraventricular tachycardia (SVT), by parent report and with medical record confirmation

Secondary Aim 4: To compare neurodevelopmental outcomes at 11 years of age in subjects randomized to a RVPAS vs. MBTS at the time of the Norwood operation.

Hypothesis: Impaired neurodevelopment will not be associated with Norwood shunt type but mean scores will be lower in single ventricle patients compared to the normative population.

Outcomes:

- Achievement, as measured by the Wechsler Individual Achievement Tests (WIAT) (Math and Reading)
- Intelligence, as measured by the Wechsler Intelligence Scale for Children (WISC)
- Other domains of neurodevelopmental function including assessment of language, executive function, visual spatial skills, motor function, memory, social skills, behavior, health-related quality of life (HRQoL) and adaptive function.

Secondary Aim 5: To develop risk stratification models for the following classes of long term outcomes: 1) cardiac outcomes, 2) transplant-free survival, and 3) neurodevelopmental outcomes.

Hypothesis: Long-term outcomes at 11 years will be worse for participants with a higher frequency of medical events.

Analyses for this aim will:

- Provide information about the association of events and interventions other than the randomized surgical procedure with late outcomes.
- Identify early cardiac and neurodevelopmental surrogate endpoints that might be useful in future studies of management strategies.
- Determine if correlates of long-term outcomes vary according to patient subgroup factors.

Secondary Aim 6: To collect specimens from subjects with HLHS and other single RV anomalies and their parents in whom DNA samples either were not collected previously or are of insufficient quality or quantity, to further develop the biologic specimen repository (biorepository).

Purpose: *To build on the collection of genetic material from the SVR cohort, to leverage the careful phenotyping of the SVR cohort to provide an opportunity for future phenotype-genotype studies and to make samples available for future hypothesis-driven studies aimed at identifying genetic determinants of outcome in HLHS and related single RV lesions.*

3. BACKGROUND INFORMATION

3.1 Overview

Hypoplastic left heart syndrome (HLHS) remains among the highest risk congenital cardiac malformations, with significant mortality and morbidity throughout childhood and early adulthood. Prior to 1980, when William Norwood described the palliative operation now commonly known as the Norwood procedure,^{1,2} children born with HLHS had virtually no chance of survival. By the late 1990s, early post-operative survival approached 80-85% in some centers.^{3,4} Despite this improvement, the ongoing risk of mortality in the early period, including 10-20% interstage mortality,^{5,6,7} resulted in one-year survival rates of only 60%-70%.⁸⁻¹⁰ Furthermore, among survivors, the morbidity associated with single ventricle physiology is substantial, with major negative consequences for quality of life and long-term survival.

3.2 Prior Studies

The Single Ventricle Reconstruction (SVR) trial was the first multicenter, randomized clinical trial to compare two operations in the field of congenital heart disease.^{8,11} Children with HLHS and other related single RV lesions were enrolled and randomized to receive either a MBTS or a RVPAS at the time of the initial Norwood procedure. This landmark study provided extraordinary insight not only into the consequences of both shunt types, but also into the course, treatment responses and short- and mid-term outcomes for these medically complex patients. Through the SVR Trial and SVR Extension Study (SVR II), outcomes, including but not limited to the primary outcome of transplant-free survival, have now been evaluated in this patient cohort when the last enrolled patient reached 12 months and again at 3 years of age. While early post-operative transplant-free survival during the interstage period⁷ and at one year⁸ was better for those children randomized to a RVPAS, survival by the 3-year evaluation appeared equivalent between the two shunt types. Moreover, RVEF was somewhat diminished and the number of interventions was higher in the RVPAS group.¹² These findings raised concern that the RV dysfunction in the RVPAS group may be progressive, leading to significantly worse long-term outcomes; if so, the benefits of the RVPAS for short-term survival may be outweighed by longer-term morbidity and mortality. Thus, the optimal surgical approach for newborns with HLHS and related single RV lesions remains unclear.

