7.1.2. Analyses of Secondary Outcomes

7.1.2.a Additional Measures of the Primary Aim

For all additional CMR and echo measures related to Aim 1, the distribution of each measure will be assessed. Continuous measures will be compared between randomized shunt types with either a Student's t-test or a Wilcoxon rank sum test as appropriate. Categorical measures will be compared with a Fisher exact test, Chi-square test or the Mantel-Haenszel test for trend.

In addition, subjects with CMR and echo performed within a 6 month window without an intervening cardiac procedure will be selected to assess the agreement between the two techniques. The continuous measures will be compared using Bland-Altman limits of agreement and Pearson's correlation coefficient. The Kappa statistic will be used to evaluate the agreement in the categorical measures in Echo and CMR.

7.1.2.b Secondary Aim 1: To compare the long-term death/transplant rates of subjects randomized to receive either a RVPAS vs a MBTS

Transplant-free survival rate will be calculated using the Kaplan-Meier method. The logrank test will be performed to determine if time since randomization to the composite endpoint of death or transplantation is different between the two shunt types. Cox proportional hazard regression will be used to model the time to death or transplant by shunt type; to determine if the shunt difference varies by time and to identify risk factors of the endpoint.

In addition, nonparametric competing-risks methodology will be used to estimate the cumulative incidence rate of death and transplant. Proportional subdistribution hazards model will be fit to assess the effect of covariate on death and transplant in a competing risk setting.

7.1.2.c Secondary Aim 2: To compare exercise tolerance between those randomized to receive a RVPAS vs a MBTS

VO₂ max, work rate VAT and items 4-11 from section 4.3.2.b, from ramped cycle ergometry will be compared between the two shunt groups. The distribution of the variable will be determined with descriptive statistics. If the variable is normally distributed, Student's t-test will be used to compare shunt groups. If non-parametric, then Wilcoxon Rank-Sum will be used.

7.1.2.d Secondary Aim 3: To compare the incidence of atrial and ventricular arrhythmias between those randomized to receive a RVPAS vs a MBTS at the time of the Norwood operation

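### Secondary Aim 1 expects a shunt effect that changes over time, but no planned summary totals transplant-free time and the plan does not say which result would then answer the early-gain, late-loss question

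*Combined protocol and SAP*

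**What the plan says.** Section 3.2 gives the history. Early transplant-free survival, through one year, "was better for those children randomized to a RVPAS, survival by the 3-year evaluation appeared equivalent between the two shunt types". The section then raises the possibility that "the benefits of the RVPAS for short-term survival may be outweighed by longer-term morbidity and mortality". The arm-specific rates at one and three years are not given.

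Section 2.2 states the Secondary Aim 1 hypothesis: "The incidence of death or cardiac transplant will be higher in the RVPAS group compared to the MBTS group". Its outcomes include the death-or-transplant composite over all follow-up, a fixed-time outcome ("Survival at 11 years post-randomization and when the last enrolled subject is 11 years old"), and freedom from the composite by 11 years among those who lived past the first year.

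Section 7.1.2.b sets out the analysis:
- Kaplan-Meier estimates of survival free of transplant.
- For the comparison by shunt: "The logrank test will be performed to determine if time since randomization to the composite endpoint of death or transplantation is different".
- Cox regression is to be used, among other purposes, "to determine if the shunt difference varies by time".
- Cumulative incidence of death and of transplant, with a subdistribution hazards model.

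Section 7.3 states power for one hazard ratio, 0.67, illustrated by 50% versus 63% transplant-free at study end. The synopsis says the follow-up is "required to determine the optimal shunt approach for children with HLHS". No section plans restricted mean survival time or another measure of net transplant-free time. None says how the shunt comparison will be reported if the effect is found to change over time.

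**The concern.** If one arm leads at one year and the curves meet by year three, that arm had the higher hazard in between. Proportional hazards was therefore already doubtful for this comparison. The logrank test and a single hazard ratio compare event rates averaged over the follow-up observed. They do not weigh years gained early against years lost later, and with crossing hazards their value shifts with the length of follow-up. The time-variation check can show that the effect changes, but not which shunt leaves children with more transplant-free time. An 11-year rate ignores time gained before year 11.

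The conditional outcome is the most exposed. It drops the first year, where the RVPAS benefit lay, and compares groups selected by survival after randomization. Read beside a hypothesis of RVPAS harm, and without a net measure next to it, it could be taken as the answer to the Section 3.2 question.

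**Working it through.** **The plan's own figure.** The implied hazard ratio is ln(0.63)/ln(0.50) = 0.667, matching the stated 0.67. With 549 children, 1:1 allocation (assumed) and no loss or crossover, events = 549 × (0.50 + 0.37)/2 = 239. Power by Schoenfeld's formula with 0.67 is Φ(0.4005 × √239/2 − 1.96) = 87.2%. The stated figure of about 80% allows for loss and crossover at rates not given. It is consistent but cannot be confirmed, and it is not disputed here.

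**Crossing hazards.** If survival is equal at three years, the RVPAS cumulative hazard over years 1-3 exceeds the MBTS one by ln[S_RVPAS(1)/S_MBTS(1)]. With an assumed 74% versus 64% at one year, that excess is ln(0.74/0.64) = 0.145.

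**One illustrative set of curves (assumed).** RVPAS is 74/66/52% and MBTS 64/63/59% at 1/3/11 years, with constant hazard within each interval, 274 per arm and censoring uniform over 11-15 years. The levels are in line with the 60-70% one-year rates in Section 3.1 and with 334/549 = 61% transplant-free survivors in Section 7.2. The area in an interval is (S_start − S_end)/λ, with λ = ln(S_start/S_end)/length.
- RVPAS to 11 years: 0.26/0.3011 + 0.08/0.0572 + 0.14/0.0298 = 0.863 + 1.399 + 4.698 = 6.960 years.
- MBTS to 11 years: 0.36/0.4463 + 0.01/0.00787 + 0.04/0.0082 = 0.807 + 1.270 + 4.878 = 6.955 years.
- Difference: +0.005 years, with a standard error of about 0.42.
- With the last hazards continued, years 11-15 add 1.961 and 2.322 years, so the difference to 15 years is 8.921 − 9.277 = −0.36 years.
- Over all follow-up, the overall hazard ratio is about 1.17. The chance of a significant logrank result against RVPAS is about 23%.

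With RVPAS at 74/65/56% and the same MBTS curve, the difference is +0.13 years at 11 and −0.04 at 15, with a hazard ratio of about 1.04.

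**Net time set exactly equal.** Assumptions: one-year gap 4-10 points, equal survival at three years, MBTS 59-60% at 11 years, N = 549, 1:1, censoring uniform over 10-15 years, two-sided 0.05. The chance shown is for a significant logrank result against RVPAS (nominal 2.5%).

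| Net time equal to | Late RVPAS loss | Hazard ratio | Chance |
|---|---|---|---|
| 11 years | even from year 3 | 1.02-1.05 | 3.3-5.5% |
| 11 years | starts year 7-8 | 1.06-1.31 | 7-57% |
| 15 years | any of these | 0.98-1.01 | 1.7-3.1% |

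The second row needs a late RVPAS hazard about 4 to 34 times the MBTS hazard. In one such setting (gap 10 points, onset year 7, logrank on all follow-up), 3000 simulated trials gave 28.5% for the logrank test and 2.7% for a test of the 11-year restricted mean.

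**The conditional outcome.** In the first illustration, freedom at 11 years among one-year survivors is 0.52/0.74 = 70.3% versus 0.59/0.64 = 92.2%. The one-step logrank hazard ratio is about 3.5 (Z about 5.7, all follow-up). The ratio of cumulative hazards to 11 years is ln(0.703)/ln(0.922), about 4.3. Net time to 11 years is equal by construction. In the equal-time settings with loss from year 3, the conditional hazard ratio is about 1.6 to 4.2.

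**The case against.** The best defence is that Secondary Aim 1 is framed as a comparison of incidence, and Kaplan-Meier, logrank and cumulative incidence address incidence. The Section 3.2 sentence is background and also covers morbidity, which survival time cannot settle. The optimal-shunt judgement rests on the whole study, whose primary outcome is RVEF. The time-variation check and the curves would expose opposing early and late effects. All of this stands, and it is why the logrank test should stay. What it leaves open is which result answers the trade-off once variation is found.

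A reader might infer that a logrank result against RVPAS would be false because net time is equal. The documents do not support that. They give no arm-specific curves, and equality at 11 years in the illustration becomes an RVPAS loss of 0.36 years by year 15, within the follow-up the composite uses. In 2000 simulated trials under the first illustration, a significant logrank result against RVPAS coincided with a restricted-mean estimate favouring RVPAS in only 0.2%. The plan's own target effect is also real net harm: if the curves are equal at 63.5% at three years and end at 50% versus 63% at 15, RVPAS loses 0.66 to 0.81 years.

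A reader might also infer that the overall hazard ratio should be dropped and the 11-year restricted mean made decisive. That does not follow either. The sign can change with the horizon, and a standard error of 0.42 years gives a 95% interval of about ±0.82 years.

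**Conclusion.** The point holds as a cheap improvement, not as a flaw that undermines the aim. The protocol's own history makes proportional hazards doubtful. It raises a net question, plans no measure of net transplant-free time, and does not say how a time-varying effect will be reported. For the overall comparison, disagreement between hazard ratio and net time is slight if late loss is gradual and absent if time is equal to 15 years. It is large only with late, steep RVPAS loss and an 11-year cut-off. The conditional outcome can mislead more strongly.

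These sizes rest on assumed one-year gaps, three-year levels, late hazards, 1:1 allocation and uniform censoring. Crossing hazards rests on reading the reported three-year equivalence as curves that met.

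**What to change.** In Section 7.1.2.b:
- Keep the logrank test and the overall hazard ratio.
- Add the intention-to-treat difference in restricted mean transplant-free survival time from randomization, with 95% confidence interval, at 11 years and at one later pre-specified horizon supported by follow-up in both groups. Sections 2.2 and 7.3 give follow-up as 10-15 and 10-16 years; reconcile these before fixing the later horizon.
- Report hazard ratios for 0-1, 1-3 and beyond 3 years as the output of the planned time-variation check, beside the overall one, with the later periods labelled descriptive.
- State that, if the effect varies over time, the trade-off will be interpreted from the restricted-mean differences at both horizons together with the Kaplan-Meier curves.
- Label the outcome among children surviving past one year as not a randomized comparison.

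The cost is analysis-plan wording and one standard analysis of data already collected. The downsides are that horizons must be fixed in advance, a second survival summary is reported, and the restricted-mean estimate will be imprecise.
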